3.5. Method of Assigning Patients to Treatment Groups

Using the interactive response system (IRS), patients will be randomized 1:1 to the patisiran or placebo arm. Randomization will be stratified by:

1. Baseline tafamidis (yes vs no)
2. Genotype (hATTR vs wtATTR amyloidosis with cardiomyopathy)
3. NYHA Class I or II and age < 75 years vs all other

Each patient will be uniquely identified in the study by a combination of the site number and patient identification number. Upon signing the informed consent form (ICF), the patient will be assigned a patient identification number by the IRS. The Investigator or his/her designee will contact the IRS to randomize the patient after confirming that the patient fulfills all the inclusion criteria and none of the exclusion criteria.

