7.1. Determination of Sample Size

The planned enrollment for this study is 300 patients. For the change from baseline at Month 12 in the 6-MWT, assuming a treatment difference of 33 meters between patisiran and placebo in the treatment-naïve group and 20 meters in patients with baseline tafamidis, the weighted average treatment difference between patisiran and placebo in the overall population is approximately 29 meters (standard deviation = 75 meters) assuming 70% are in the treatment-naïve group and 30% are in the baseline tafamidis group. A sample size of 300 patients provides >90% power for a 2-sided test to detect a mean difference between treatment groups at a 2-sided alpha = 0.05. Additional patients may be enrolled based on a recommendation to increase the sample size in the interim assessment (Section 7.2.10).

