7.2.5.1. Primary Endpoint

The primary endpoint, change from baseline at Month 12 in the 6-MWT, will be analyzed using a mixed-effects model repeated measures (MMRM) approach. The outcome variable is change from baseline in the 6-MWT. The model will include the baseline value as a covariate, treatment, visit, baseline tafamidis (yes vs no), genotype (hATTR vs wtATTR), age (<75 vs ≥ 75 years), the treatment-by-visit interaction, the treatment-by-baseline tafamidis interaction, the visit-by-baseline tafamidis interaction, and the treatment-by-visit-by-baseline tafamidis

interaction as fixed factors. The primary comparison is the contrast (difference in least squares [LS] means) between the patisiran and placebo groups at Month 12.

Sensitivity analyses will be detailed in the SAP.

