7.2.5.2. Secondary Endpoints

Secondary endpoints are described in Section 2.

KCCQ-OS will be analyzed using a similar MMRM model as used for the primary endpoint.

The composite endpoint of all-cause mortality, frequency of CV events (CV hospitalizations and urgent HF visits) and change from baseline in 6-MWT will be analyzed using a generalized rank-based win ratio method, which makes pairwise comparisons (for all possible patisiran/placebo patient pairs) of the 3 components in the hierarchical order specified above. The point estimate for the win ratio is defined as the total number of better outcomes divided by the total number of worse outcomes in the patisiran group. The detailed algorithm for assessment of this endpoint will be provided in the SAP.

The composite endpoint of all-cause mortality and frequency of all-cause hospitalizations and urgent HF visits will be analyzed using a modified Andersen-Gill model stratified by baseline tafamidis (yes vs no), including treatment, genotype (hATTR vs wtATTR), NYHA Class (I/II vs III), and age (<75 vs \geq 75 years) as covariates.

Patients who undergo a heart transplantation and/or ventricular assist device placement after randomization will be handled in the same manner as death in the primary analyses of mortality related endpoints.

Deaths and hospitalizations due to COVID-19 will be excluded from the primary analyses of endpoints involving all-cause death and/or all-cause hospitalizations. Analyses of the individual components of the composite endpoints will be detailed in the SAP.

To control the overall Type I error rate, secondary endpoints will be tested in a prespecified hierarchical order.

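### The primary 6-MWT model carries only the age half of the combined NYHA/age stratification factor, which gives up a small amount of precision

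*Protocol*

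**What the plan says.** Protocol 3.5 (and the synopsis) stratifies the 1:1 randomisation by three factors. Two are baseline tafamidis and genotype. The third is one two-level factor: "NYHA Class I or II and age < 75 years vs all other".

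Protocol 7.2.5.1 (and the synopsis) lists the terms of the primary MMRM. Besides baseline 6-MWT, treatment, visit and the interactions among treatment, visit and tafamidis, the patient-level factors are "baseline tafamidis (yes vs no), genotype (hATTR vs wtATTR), age" (<75 vs ≥75 years). Neither NYHA class nor the combined factor appears.

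Protocol 7.2.5.2 says that KCCQ-OS will use an MMRM similar to the primary one and lists no covariates for it. For the composite of all-cause mortality, all-cause hospitalisations and urgent HF visits, the same section specifies a modified Andersen-Gill model stratified by tafamidis, with covariates that include "genotype (hATTR vs wtATTR), NYHA Class (I/II vs III), and age".

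Protocol 7.1 states: "A sample size of 300 patients provides >90% power for a 2-sided test".

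**The concern.** An analysis should normally reflect the factors used to randomise. Here two of the three are in the primary model and the third is there only in part. Class IV is excluded at screening (4.2), so among patients under 75 the combined factor is exactly NYHA I/II versus III. That split appears nowhere in the MMRM.

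The protocol treats NYHA class as worth adjusting for in one confirmatory analysis and leaves it out of the primary one without comment. NYHA class is graded by symptoms on ordinary activity, walking included (10.2), so it could plausibly predict change in walking distance. If it does so beyond the covariates already present, leaving it out widens the confidence interval for the primary comparison and costs some power. The same would apply to KCCQ-OS if its model copies the primary one.

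**Working it through.** **Inputs from Protocol 7.1.** Treatment differences of "33 meters between patisiran and placebo in the treatment-naïve group and 20 meters in patients with baseline tafamidis"; mix "assuming 70% are in the treatment-naïve group and 30% are in the baseline tafamidis group"; the overall difference "is approximately 29 meters (standard deviation = 75 meters"; 300 patients, two-sided alpha 0.05. With 1:1 allocation (3.5) this is 150 per arm.

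**Reproducing the plan's figure.**
- Weighted difference: 0.7 × 33 + 0.3 × 20 = 29.1 m, stated as about 29 m.
- Standard error: 75 × √(2/150) = 8.66 m.
- Power: Φ(29/8.66 − 1.96) = 91.8% (91.9% at 29.1 m; 91.6% at 29 m with the noncentral t).

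The statement of more than 90% holds. It is a plain two-sample calculation with SD 75 m and takes no credit for any covariate, so it does not depend on whether NYHA is in the model.

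**Value of adding NYHA.** Let R² be the share of residual Month 12 variance that NYHA explains beyond baseline 6-MWT, age, genotype and tafamidis. The protocol gives no value, so R² is an assumed range. The standard error becomes 8.66 × √(1 − R²), and the equivalent sample size is 300/(1 − R²).

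| Assumed R² | SE (m) | Power at 29 m | Gain (points) | Equivalent N |
|---|---|---|---|---|
| 0% | 8.66 | 91.8% | 0 | 300 |
| 1% | 8.62 | 92.0% | 0.3 | 303 |
| 2% | 8.57 | 92.3% | 0.5 | 306 |
| 5% | 8.44 | 93.0% | 1.2 | 316 |
| 10% | 8.22 | 94.2% | 2.4 | 333 |

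Gains are taken from unrounded powers.

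**Type I error under the actual scheme.** A simulation used 300 patients, randomisation balanced within the two levels of the combined factor, and a single-time-point linear model with treatment and age, with or without NYHA. It assumed 40% of patients under 75 and 15% in Class III, with 10,000 runs per setting.

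| Assumed R² | Type I error, NYHA omitted | Type I error, NYHA included | Power gain from including NYHA |
|---|---|---|---|
| 2% | 4.85% | 4.91% | 0.4 points |
| 5% | 5.04% | 4.98% | 1.1 points |
| 10% | 4.94% | 4.95% | 2.5 points |

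Runs under other assumed mixes (40–50% under 75, 15–30% in Class III) gave about 4.5% to 5.2% with NYHA omitted. The power gains agree with the formula.

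**The case against.** The strongest case for leaving the model alone has four parts.

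- **Most of the design is already reflected.** Tafamidis, genotype and the age half of the third factor are in the model. Only the NYHA split among patients under 75 is missing. This stands.
- **Baseline 6-MWT may already carry most of what NYHA knows.** It measures walking capacity directly. Eligibility also narrows the NYHA range: Class IV is excluded, as is Class III with disease Stage 3, and at least 150 m on the screening walk is required. This stands too. The true R² may be near zero, and nothing in the protocol supports a value of 5–10%.
- **Different endpoints may have different covariates.** The Andersen-Gill model has no baseline functional measure, so NYHA can serve there as the severity adjuster. This softens the contrast between the two models but does not explain why part of a randomisation factor is left out of the primary analysis.
- **The KCCQ-OS covariates are not listed.** Omission there is implied by the reference to a similar model, not stated.

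A reader might go further and infer that omitting a stratification factor makes the reported standard error too large for the design, so that the primary test is conservative. That would require randomisation to balance the omitted variable. It does not: every patient aged 75 or over falls in the second level of the combined factor whatever the NYHA class, so NYHA is balanced only under 75. The simulations show no material departure from 5%.

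**Conclusion.** The mismatch is real: the primary MMRM carries two randomisation factors and half of the third, while another confirmatory model in the same protocol adjusts for NYHA class. Its effect is limited to a small loss of precision. For an assumed R² of 0 to 10%, adding NYHA is worth 0 to about 2.4 points of power, from 91.8% to at most about 94.2%. The range rests on the protocol's 29 m, SD 75 m and 150 per arm, and on an R² that the protocol does not supply.

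The omission does not invalidate the primary test, does not materially change its type I error and does not undermine the sample-size statement. For KCCQ-OS the point is conditional on that model following the primary one. The change is worth making because it costs almost nothing and aligns the analysis with the randomisation.

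**What to change.** Before unblinding, amend 7.2.5.1 and the matching synopsis text to include, as a fixed effect, one of:

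- NYHA class (I/II vs III) alongside age, using the coding already given for the Andersen-Gill model; or
- the combined randomisation factor (NYHA I/II and age <75 vs all other), kept together with age.

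The first adjusts for NYHA at all ages and is the option that the power figures describe. The second mirrors the randomisation exactly but captures NYHA only under age 75, so any gain in precision may be smaller. State in 7.2.5.2 that the KCCQ-OS MMRM carries the same term. If the sponsor prefers to leave NYHA out, give the reason.

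The cost is a line of wording and about one degree of freedom among 300 patients. NYHA class is already collected at screening. A change made after unblinding would be open to challenge as data-driven.

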3. INVESTIGATIONAL PLAN

3.1. Summary of Study Design

This is a Phase 3, randomized (1:1), double-blind, placebo-controlled, multicenter study to evaluate the efficacy and safety of patisiran in approximately 300 patients with ATTR amyloidosis (hereditary or wt) with cardiomyopathy. Approximately 20% of the study population is anticipated to have hATTR and 80% wtATTR. In addition, at baseline, patients are either:

- Tafamidis naïve; or
- Currently on tafamidis (for ≥ 6 months), with disease progression in the opinion of the Investigator. This group will be capped at 30% of total enrollment in the study.

In addition to patients who have never taken tafamidis, patients who have been on tafamidis for ≤ 30 days total and have not received any tafamidis in the 6 months prior to baseline will be considered tafamidis naïve for this study.

The study consists of a screening period of up to 45 days, a 12-month, double-blind, placebo-controlled period, a 36-month, open-label extension period (during which all patients will receive patisiran), and a 28-day follow-up period ([Figure 1](#)).

After screening, during the 12-month double-blind period, eligible patients will be randomized to receive IV treatment every 3 weeks with either patisiran (0.3 mg/kg for patients weighing <100 kg; 30-mg fixed dose for patients weighing ≥ 100 kg) or placebo. Prior to receiving randomized, double-blind study drug (patisiran or placebo), to reduce the potential for an IRR with patisiran, all patients will receive premedications at least 60 minutes before the start of their infusion. (Patients randomized to placebo will also receive premedications to maintain the blind.) Study drug will be administered as an approximately 80-minute IV infusion.

During the open-label extension period, all patients will receive treatment with open-label patisiran.

Study drug administration at a location other than the study center (eg, at home) may be administered as follows:

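### Since Amendment 3 the primary LS-mean contrast depends on the weights given to the two tafamidis strata, and the protocol names none; under the usual equal-weight convention it would not match the powered 29 m and >90%

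*Protocol*

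**What the plan says.** Section 7.2.5.1 analyses the change in 6-MWT with an MMRM. Its fixed factors now include "the treatment-by-baseline tafamidis interaction" and the three-way term with visit. The test itself is described as follows: "The primary comparison is the contrast (difference in least squares [LS] means) between the patisiran and placebo groups at Month 12". Nothing in the section, or in the matching synopsis text, says how the two tafamidis strata are combined into one difference.

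Section 7.1 sets the power on a combined effect. It starts from two stratum effects, "assuming a treatment difference of 33 meters between patisiran and placebo in the treatment-naïve group and 20 meters in patients with baseline tafamidis", and combines them "assuming 70% are in the treatment-naïve group and 30% are in the baseline tafamidis group". The result is that "the weighted average treatment difference between patisiran and placebo in the overall population is approximately 29 meters (standard deviation = 75 meters"). It concludes that "A sample size of 300 patients provides >90% power for a 2-sided test" "at a 2-sided alpha = 0.05".

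On the smaller stratum, section 3.1 says: "This group will be capped at 30% of total enrollment in the study". The 30% used for planning is therefore the upper limit of that share.

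The protocol dated 22 May 2020 had baseline tafamidis as a main effect only. The Amendment 3 summary gives the reason for the change: to let the treatment effect differ between the tafamidis subgroups. The sentence on the primary comparison and the sample-size figures are the same in both versions.

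**The concern.** In a model where tafamidis is only a main effect, there is one treatment difference at Month 12, and averaging over tafamidis levels drops out of it. With complete data, a common SD and 1:1 allocation within strata, that model weights each stratum by its size, which is the average that 7.1 powers. Once treatment interacts with tafamidis, there are two Month 12 differences, and an overall one exists only after weights are chosen. Genotype and age have no interaction with treatment, so their weights still cancel; the issue is confined to tafamidis.

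An LS mean requested without qualification is conventionally an equal average over the levels of a class factor. Followed that way, the sentence gives half the weight to a stratum that may hold at most 30% of patients and for which the plan assumes the smaller effect. The estimate would then not describe the enrolled mix, and its standard error would be larger. At stake is which quantity the primary test estimates, and with what power. Section 7.2.5 makes all testing of secondary endpoints conditional on that test. If the weights are still open at analysis, there are also two candidate primary p-values.

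**Working it through.** **Inputs.** From 7.1: effects of 33 m (naïve) and 20 m (baseline tafamidis), SD 75 m, N = 300, shares 70/30, two-sided alpha 0.05. From 3.5: 1:1 randomization, stratified by baseline tafamidis, so 150 per arm, made up of 105 naïve and 45 on tafamidis. Assumptions added here: SD 75 m within each stratum and no dropout (the protocol states no dropout rate).

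**Reproducing the plan's figure.** Combined effect: 0.7 × 33 + 0.3 × 20 = 29.1 m. SE = 75 × √(2/150) = 8.66 m. Power = Φ(29.1/8.66 − 1.96) = 91.9%; with the rounded 29 m it is 91.8%. The stated figure of more than 90% reproduces.

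**Contrast in the interaction model.** With weight w on the tafamidis stratum and per-arm stratum sizes n_N and n_T:

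- effect = (1 − w) × 33 + w × 20
- variance = 75² × [(1 − w)² × 2/n_N + w² × 2/n_T]
- power = Φ(effect/SE − 1.96)

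*Observed weights, w = 0.30:* variance = 5625 × (0.49 × 2/105 + 0.09 × 2/45) = 75.0, SE 8.66 m, effect 29.1 m, power 91.9%. This agrees with 7.1.

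*Equal weights, w = 0.50:* effect = (33 + 20)/2 = 26.5 m. Variance = 0.25 × 5625 × (2/105 + 2/45) = 89.3, SE 9.45 m. Power = Φ(26.5/9.45 − 1.96) = 80.1% (79.8% with a noncentral t).

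**Where the loss comes from.** The smaller effect with the original SE gives Φ(26.5/8.66 − 1.96) = 86.4%. The larger SE with the original effect gives Φ(29.1/9.45 − 1.96) = 86.9%; the variance inflation is 1/(4 × 0.3 × 0.7) = 1.19. The two sources are of similar size. About 402 patients would restore 90% power under equal weights.

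**Shares below the cap** (25% and 20% are assumed for illustration):

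| Tafamidis share | Equal weights: effect, SE, power | Observed weights: effect, SE, power |
|---|---|---|
| 30% | 26.5 m, 9.45 m, 80.1% | 29.1 m, 8.66 m, 91.9% |
| 25% | 26.5 m, 10.0 m, 75.5% | 29.75 m, 8.66 m, 93.0% |
| 20% | 26.5 m, 10.8 m, 68.7% | 30.4 m, 8.66 m, 93.9% |

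As the stratum shrinks, equal-weight power falls while observed-weight power rises slightly.

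**The case against.** A reader might infer that the protocol has adopted a 50/50 average and that the trial therefore has only 80% power. The documents do not support this. They nowhere call the contrast unweighted or equally weighted, and they name no software option. LS means are not equal-weight by definition, since the same quantity can be computed with observed margins. The only place where the protocol discusses combining the strata is 7.1, which uses population shares. Reading 7.2.5.1 in that light makes the two sections agree. Section 7 also leaves implementation to the SAP, which was not available and may already give the weights.

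All of that stands, and it is why the point concerns unstated weights rather than a wrong choice. It does not remove the point. The weights determine what the primary comparison estimates, so they are more than a computing detail such as the degrees-of-freedom method. The protocol fixes both the powered quantity and the tested quantity, and taking the tested one in its ordinary sense does not yield the powered one.

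A second tempting inference is that KCCQ-OS has the same problem. Section 7.2.5.2 says only that its model is similar, so it is not established that the tafamidis interactions are carried over. Finally, type I error is not at issue: with no effect in either stratum, both contrasts have expectation zero.

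**Conclusion.** The point holds as an unresolved choice with a material consequence. Under the plan's own assumptions, one sentence in 7.2.5.1 can be carried out in two ways: 29.1 m with about 92% power, which fits 7.1, or 26.5 m with about 80% power, which does not. The second follows from the usual convention when no weights are requested. The type II error is about 8% in one case and 20% in the other.

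The figures depend on a common SD of 75 m in both strata, complete data, and the full 30% tafamidis share. The first two assumptions affect the exact values but not the kind of discrepancy. The third is the most favourable case for equal weights, because the share cannot exceed 30%. The difference in effect size also depends on the plan's assumed 33 m and 20 m. If the stratum effects were equal, only the loss of precision would remain.

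**What to change.** In 7.2.5.1 and the synopsis, state before unblinding that the Month 12 LS-mean difference is averaged over baseline tafamidis using the observed proportions in the FAS, or fixed 70/30 weights. Apply the same sentence to KCCQ-OS if its model carries the same interactions. Report the two stratum-specific differences as supportive.

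If equal weights are intended, restate the effect and power in 7.1 as about 26.5 m and 80% for 300 patients.

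The first route costs one sentence in each place and one option in the analysis program. It needs no extra patients and does not affect type I error when set before unblinding. If the SAP already gives observed or 70/30 weights, the protocol text only needs to be brought into line with it.

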7.2.5.2. Secondary Endpoints

Secondary endpoints are described in Section 2.

KCCQ-OS will be analyzed using a similar MMRM model as used for the primary endpoint.

The composite endpoint of all-cause mortality, frequency of CV events (CV hospitalizations and urgent HF visits) and change from baseline in 6-MWT will be analyzed using a generalized rank-based win ratio method, which makes pairwise comparisons (for all possible patisiran/placebo patient pairs) of the 3 components in the hierarchical order specified above. The point estimate for the win ratio is defined as the total number of better outcomes divided by the total number of worse outcomes in the patisiran group. The detailed algorithm for assessment of this endpoint will be provided in the SAP.

The composite endpoint of all-cause mortality and frequency of all-cause hospitalizations and urgent HF visits will be analyzed using a modified Andersen-Gill model stratified by baseline tafamidis (yes vs no), including treatment, genotype (hATTR vs wtATTR), NYHA Class (I/II vs III), and age (<75 vs \geq 75 years) as covariates.

Patients who undergo a heart transplantation and/or ventricular assist device placement after randomization will be handled in the same manner as death in the primary analyses of mortality related endpoints.

Deaths and hospitalizations due to COVID-19 will be excluded from the primary analyses of endpoints involving all-cause death and/or all-cause hospitalizations. Analyses of the individual components of the composite endpoints will be detailed in the SAP.

To control the overall Type I error rate, secondary endpoints will be tested in a prespecified hierarchical order.

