4.2. Exclusion Criteria

Patients are excluded from the study if any of the following criteria apply:

Disease-specific Conditions

1. Has known primary amyloidosis (AL) or leptomeningeal amyloidosis.
2. NYHA Class III **AND** ATTR amyloidosis disease Stage 3 (defined as both NT-proBNP >3000 ng/L and estimated glomerular filtration rate [eGFR] <45 ml/min/1.73 m²).[\[Gillmore 2018\]](#)
3. NYHA Class IV at the Screening visit.
4. Has a polyneuropathy disability (PND) Score IIIa, IIIb, or IV (requires cane or stick to walk, or is wheelchair bound) at the Screening visit.

Laboratory Assessments

5. Has any of the following laboratory parameter assessments at screening:
 - a. Aspartate transaminase (AST) or alanine transaminase (ALT) levels $>2.0 \times$ the upper limit of normal (ULN).
 - b. Total bilirubin $>2 \times$ ULN.

- c. International normalized ratio (INR) >1.5 (unless patient is on anticoagulant therapy, in which case excluded if INR >3.5).
- 6. Has eGFR <30 mL/min/1.73 m² (using the modification of diet in renal disease [MDRD] formula).
- 7. Has known human immunodeficiency virus infection; or evidence of current or chronic hepatitis C virus or hepatitis B virus infection.

Prior/Concomitant Therapy

- 8. Tafamidis naïve patients (at baseline) for whom the Investigator actively plans or anticipates commencing treatment with tafamidis during the 12-month double-blind period, taking into consideration clinical status, patient preference and/or commercial availability of tafamidis.
- 9. Is currently taking diflunisal; if previously on this agent, must have at least a 30-day wash-out prior to dosing (Day 1).
- 10. Is currently taking doxycycline, ursodeoxycholic acid, or taurooursodeoxycholic acid; if previously on any of these agents, must have completed a 30-day wash-out prior to dosing (Day 1).
- 11. Received prior TTR-lowering treatment (including patisiran) or participated in a gene therapy trial for hATTR amyloidosis.
- 12. Current or future participation in another investigational device or drug study, scheduled to occur during this study, or has received an investigational agent or device within 30 days (or 5 half-lives of the investigational drug, whichever is longer) prior to dosing (Day 1). In the case of investigational TTR stabilizer drugs, washout for 6 months prior to dosing (Day 1) is required; this does not apply to patients who are on tafamidis at baseline (per inclusion Criterion 4).

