6.2.5.1. Cardiac Biomarkers

The cardiac biomarkers NT-proBNP and troponin I will be used to assess cardiac stress and heart failure severity. These biomarkers have been shown to be prognostic of outcomes in HF, including in ATTR amyloidosis.[[Damy 2016](#); [Kristen 2017](#); [Merlini 2016](#)] Blood samples will be drawn to measure cardiac biomarker levels at the timepoints specified in the Schedule of Assessments ([Table 1](#), [Table 2](#), [Table 3](#), and [Table 4](#)) and will be measured at a central laboratory. At screening Visit 1, only NT-proBNP will be assessed for eligibility purposes.

Details on cardiac biomarker sample collection, processing, and storage will be provided in a Study Laboratory Manual.

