6.2.5.2. ATTR Amyloidosis Disease Stage

Based on published data from Gillmore et al, the ATTR amyloidosis disease staging used for this protocol stratifies patients with ATTR amyloidosis with cardiomyopathy (both hATTR and wtATTR) into prognostic categories using the serum biomarkers NT-proBNP and eGFR.[[Gillmore 2018](#)] Patients are categorized as follows:

- Stage 1 (lower risk): NT-proBNP \leq 3000 ng/L and eGFR \geq 45 ml/min/1.73 m²
- Stage 2 (intermediate risk): all other patients not meeting criteria for Stages 1 or 3
- Stage 3 (higher risk): NT-proBNP $>$ 3000 ng/L and eGFR $<$ 45 ml/min/1.73 m²

Based on published data, this staging system discriminates between patients with median survival of ~6 years, ~4 years, and ~2 years for Stage 1, Stage 2, and Stage 3, respectively.

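### The Andersen-Gill model for death, hospitalization and urgent HF visits is valid but leaves out baseline ATTR disease stage, and its NYHA term cannot identify the Stage 3 patients; adding stage is a low-cost, low-priority gain in precision

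*Protocol*

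**What the plan says.** Section 7.2.5.2 gives the covariate set for the last secondary endpoint in full: the model is "stratified by baseline tafamidis (yes vs no), including treatment, genotype (hATTR vs wtATTR), NYHA Class (I/II vs III), and age", with age cut at 75 years. NT-proBNP, eGFR and the stage built from them do not appear. The same section leaves the win-ratio algorithm to the SAP, but it spells this model out.

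Section 6.2.5.2 defines stage from NT-proBNP (cut at 3000 ng/L) and eGFR (cut at 45) and states that "this staging system discriminates between patients with median survival of ~6 years, ~4 years, and ~2 years" for Stages 1, 2 and 3 respectively. Section 6.2.5.1 says of NT-proBNP and troponin I: "These biomarkers have been shown to be prognostic of outcomes in HF, including in ATTR amyloidosis".

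Section 4.2 excludes "NYHA Class III AND ATTR amyloidosis disease Stage 3" (criterion 2) and "NYHA Class IV at the Screening visit" (criterion 3). Stage 3 itself remains eligible: inclusion criterion 7 in section 4.1 admits NT-proBNP up to, but not including, 8500 ng/L, and exclusion criterion 6 removes only eGFR below 30.

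Section 3.5 stratifies randomization by baseline tafamidis, genotype, and a combined NYHA and age factor. Stage is not a stratum.

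**The concern.** The sponsor chose to adjust this endpoint for severity, but the eligibility rules prevent the chosen variable from finding the highest-risk group. With NYHA III plus Stage 3 excluded, and NYHA IV excluded outright, the NYHA III level holds only Stages 1 and 2 at screening. All Stage 3 patients share the I/II level with the mildest patients. Neither the randomization nor the model therefore balances or adjusts for the factor to which the protocol attaches the steepest survival gradient.

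This is the only endpoint in the type I error hierarchy made up solely of deaths, hospitalizations and urgent HF visits. If the arms happened to differ in their number of Stage 3 patients, the result would be questioned, and an adjustment added after unblinding would carry little weight.

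**Working it through.** **The protocol's own power figure.** The only one is for the 6-MWT (section 7.1): 29 m, SD 75 m, 150 per arm, two-sided 0.05. Standardized difference: 29 / (75 × √(2/150)) = 29 / 8.66 = 3.35. Power: Φ(3.35 − 1.96) = 0.918, which agrees with the stated figure of more than 90%. No power is stated for the Andersen-Gill composite, so there is no figure to reproduce for it.

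**Gradient implied by section 6.2.5.2.** Assuming constant hazards, hazard = ln 2 / median:

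| Stage | Median (years) | Hazard per year | Relative to Stage 1 | 12-month death risk |
|---|---|---|---|---|
| 1 | 6 | 0.116 | 1 | 10.9% |
| 2 | 4 | 0.173 | 1.5 | 15.9% |
| 3 | 2 | 0.347 | 3 | 29.3% |

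**Effect on power and type I error.** The protocol gives no stage mix, event rate or effect size for this endpoint, so all three are assumed. Two sets of simulated one-year trials (300 patients, 1:1) were run. Both used a constant-rate equivalent of the Andersen-Gill model with a patient-level sandwich variance, death ending follow-up, and no NYHA III in Stage 3.

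- *Set A* (3,000 trials per setting): about 0.6 events per patient, rate ratio 0.65, frailty variance 0.3 to 1.2, stage mix 65/28/7% to 55/33/12%; stage added to treatment, NYHA, age and genotype. With hospitalizations on the full survival gradient, power rose by 1.3 to 3.2 points (for example 71.0% to 74.2%). On half the log gradient the change was −0.4 to +1.5 points.
- *Set B* (2,000 trials per setting): placebo hospitalization rate 0.5 per year on the full gradient, rate ratio 0.6 or 0.7, stage mix 65/30/5% to 40/40/20%, frailty variance near 0 or 1; stage added to treatment and NYHA. Power rose by 1.2 to 4.4 points, for example 82.0% to 85.3% at rate ratio 0.6 with 10% Stage 3. In that setting the mean estimate was 0.603 without stage and 0.600 with it.

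Type I error was 5.3% without and 5.0% with stage in set A. In set B it was 4.6% to 5.8% without and 4.6% to 6.6% with. The Monte Carlo standard error is about 0.4 to 0.5 points. The 6.6% came from the model that includes stage, with only about 15 Stage 3 patients, and did not recur in the larger mixes.

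**Chance imbalance.** Take 12% Stage 3, that is 36 of 300. The number in one arm has SD √(36 × 0.25 × 264/299) = 2.8, and the exact hypergeometric chance of a 23:13 split or worse, in either direction, is 10.9%. With a 55/33/12% mix the other stages average (55 × 1 + 33 × 1.5)/88 = 1.19 on the full gradient.

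- Full gradient: (23 × 3 + 127 × 1.1875) / (13 × 3 + 137 × 1.1875) = 219.8 / 201.7 = 1.09.
- Half the log gradient (Stage 3 = √3 = 1.73; others average (55 + 33 × √1.5)/88 = 1.08): 177.5 / 171.1 = 1.04.

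Such a split therefore moves the unadjusted rate ratio by about 4% to 9%. Allowing for imbalance in all three stages on the full gradient, the 95% range of the shift is about 8% to 11% either way over stage mixes from 65/30/5% to 40/40/20%.

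**The case against.** The best defense is that nothing here is an error. The terms in the model are the variables from which the randomization strata are built, which is a conventional and defensible choice. The protocol never offers NYHA as a substitute for stage. No stated power is missed, and this endpoint comes last in the sequence, so it is tested only if the primary and two earlier secondaries succeed. That stands, and it is why the priority is low.

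A reader might infer that the omission biases the comparison, inflates type I error or shrinks the treatment effect toward the null. The protocol does not support that. Randomization protects the test, chance imbalance is part of the variation that the standard error already covers, and in a log-rate model with these inputs the estimate hardly moves (0.603 against 0.600).

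The size of the gain is also open to challenge. The stated gradient concerns survival. Nothing in the protocol says that all-cause hospitalizations, which would supply most events, follow it. Enrolled Stage 3 patients are also a selected group (clinically stable, at least 150 m on the walk test, NT-proBNP and eGFR limits, not NYHA III or IV), so the 1 : 1.5 : 3 ratio may overstate the gradient within the trial. Both points stand; the half-gradient results show what they do to the figures.

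The SAP, not shown here, may contain a stage-adjusted supportive analysis. That would help interpretation but would not change the confirmatory model that the protocol fixes.

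**Conclusion.** The point holds as a matter of efficiency. The confirmatory model omits the baseline factor that the protocol itself describes as strongly prognostic, and its one severity term cannot identify Stage 3. The cost is modest: about 1 to 4 power points if hospitalizations follow the survival gradient, close to nil at half the log gradient, plus a possible shift of about 4% to 9% in the unadjusted rate ratio at a Stage 3 split with roughly an 11% chance.

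These sizes rest on an assumed stage mix, event rate, frailty and effect, on constant hazards, and on a constant-rate stand-in for the Andersen-Gill model.

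Two limits apply to the NYHA argument. It holds at screening, by eligibility, and a NYHA III patient near a cut-off could move into Stage 3 by Day 1. NYHA may also still partly separate Stage 1 from Stage 2; the gap concerns Stage 3.

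**What to change.** In section 7.2.5.2, before unblinding, add baseline ATTR amyloidosis disease stage (1, 2, 3) as a prespecified covariate in the modified Andersen-Gill model. Keep the tafamidis stratification and the genotype, NYHA and age terms.

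The cost is one phrase and two model terms. No new data are needed: NT-proBNP and eGFR are required at screening for eligibility, and change from baseline in stage is already an exploratory endpoint, so baseline stage is collected. Amendment 3 already revised the covariates of the primary model, so an edit of this kind is feasible. If the blinded Stage 3 count proves very small, the behavior of the robust variance with a sparse stage level should be checked before unblinding.
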